### 12.1.5 Insufficient Data for Analysis/Presentation

If there are no values or events at the general value then the break out should not be presented. For example if the number of AEs related to study procedure is zero then the presentation by severity of related events will not be produced.

Some of the TFLs will not have sufficient numbers of subjects or data for presentation. If this occurs, the blank TFL shell will be presented with a message printed in the center of the table, such as: “No applicable data for this summary.”

For categories of continuous summaries that have <4 subjects no summaries will be shown.

### 12.1.6 Handling of Unplanned and Early Termination Assessment

#### Data

Unscheduled assessments will be in general excluded from the analysis and summary statistics. However certain data planned for scheduled assessments are reported within unscheduled visit forms in the eCRF (e.g. repeated/delayed assessments). Given that it is not practical to re-assign them to the pertaining scheduled visits in the eCRF, these data will be accounted for in the analysis and summaries by applying the following re-mapping algorithm to each unscheduled visit:

- If Unscheduled visit date < enrollment date then analysis timepoint = Screening
- If Unscheduled visit date  $\geq$  enrollment date and < randomization date then analysis timepoint = Enrollment
- If Unscheduled visit date  $\geq$  randomization date then:
  1. Determine the unscheduled visit study day using the visit date until midnight.
  2. Determine the reference scheduled visit as the latest previous ( $\leq$ ) scheduled visit recorded and derive the nominal study day from Table 17.
  3. If unscheduled visit study day  $\leq$  nominal study day of the reference scheduled visit + 30 days then unscheduled visit data will be assigned to the analysis timepoint of the reference scheduled visit (see Table 2); otherwise data will be remapped to the analysis time point using the time windows described in Table 17.

For example, someone missing lab assessments at V7 but performed them at study day 123 as recorded in unscheduled form, would have unscheduled lab assessments not mapped to Month 3 (because performed 31 days later than nominal V7 study day) but mapped to Month 4 (because the unscheduled study day is in the [107, 137] time window of Month 4).

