Subjects who sign the ICF for the extension study but do not meet the entry criteria will be considered as screening failure and will enter the 28 day safety follow-up period of the original study. If the subject withdraws or is removed from the study after enrollment, he/she will enter the safety follow up period of the extension study (section 9.3).

The Extended Exposure Period (from Check-out of V10 [Week 26] until Check-out of V16 [Week 52]):

Enrolled subjects will continue to use the product they were randomized to in the original study (THS 2.2 arm or CC arm) in an ambulatory setting for an additional 26 weeks *ad libitum*, including during the visits. Subjects will continue to capture the number of each of the products used including THS Tobacco Sticks, CC (menthol and non-menthol), and other nicotine/tobacco containing products on a daily basis in a product use diary.

After V10, subjects will be required to come for 6 monthly visits to the site for resupply of THS 2.2 (except for V16) and for safety assessments. The visits will be scheduled with a time window of +/- 5 days respective to V4 of the original study:

- V11 (30 weeks after V4, 210 days +/- 5 days),
- V12 (35 weeks after V4, 245 days +/- 5 days),
- V13 (39 weeks after V4, 273 days +/- 5 days),
- V14 (43 weeks after V4, 301 days +/- 5 days),
- V15 (48 weeks after V4, 336 days +/- 5 days),
- V16 (52 weeks after V4, 364 days +/- 5 days).

Confidentiality Statement

Data and information contained in this document are considered to constitute trade secrets and confidential commercial information, and the legal protections provided to such trade secrets and confidential information are hereby claimed under the provisions of applicable law. No part of this document may be publicly disclosed without the written consent of Philip Morris Products S.A.

At V15, containers to collect 24 hour urine will be distributed to the subjects. Twenty four-hour urine collection will start in the morning of the day before V16 and will end 24 hours later on the morning of V16. At V16, blood and urine samples from the 24 hour urine collection will be collected by the site for the assessments of BoExp and clinical risk endpoints.

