**Table 17: Mapping of Visits After Randomization**

Analysis Time Point	Nominal Study Day (Study Visit and Week number)	Time Window (in Study Days) for Assessments
Day 1	1	= 1
Month 1	29 (V5, Week 4)	[2, 46]
Month 2	64 (V6, Week 9)	[47, 78]
Month 3	92 (V7, Week 13)	[79, 106]
Month 4	120 (V8, Week 17)	[107, 137]
Month 5	155 (V9, Week 22)	[138, 169]
Month 6	183 (V10, Week 26)	[170, 197]
Month 7	211 (V11, Week 30)	[198, 228]
Month 8	246 (V12, Week 35)	[229, 260]
Month 9	274 (V13, Week 39)	[261, 288]
Month 10	302 (V14, Week 43)	[289, 319]
Month 11	337 (V15, Week 48)	[320, 351]
Month 12	365 (V16, Week 52)	≥ 352

Unscheduled assessments will be labelled as unscheduled and presented together with the re-mapped analysis time point in the listings.

Early Termination Assessments will be mapped using the relative study day using the visit date until midnight. Given that Early Termination visits are in general conducted during scheduled visits, the mapping will be performed using time windows as defined in Table 17, apart from early termination visits before randomization (e.g. subjects enrolled and not randomized) which will be assigned to the Enrollment time point. Early termination visit assessments will be labelled as early termination visit and presented together with the re-mapped analysis time point in the listings.

Data from Unscheduled and Early Termination assessments will be combined with data from scheduled visits in the analysis and summary statistics only if there are not scheduled visit

data for the same parameters at that re-mapped analysis time point, and only if the data are scheduled to be collected at that analysis timepoint.

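### When V7, V10 or V16 is not yet on record, the 30-day carry-back for unscheduled visits sends most in-window primary-endpoint values to the preceding month, where they are excluded

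*SAP*

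**What the plan says.** SAP Section 12.1.6 excludes unscheduled assessments in general, but makes an exception because "certain data planned for scheduled assessments are reported within unscheduled visit forms in the eCRF (e.g. repeated/delayed assessments"). After randomization the exception works in this order:

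- Step 2 says to "Determine the reference scheduled visit as the latest previous" scheduled visit on record. A visit on the same day counts.
- Step 3 compares the unscheduled study day with the "nominal study day of the reference scheduled visit + 30 days then unscheduled visit data will be assigned to the analysis timepoint" of that reference visit. If the day is later, "otherwise data will be remapped to the analysis time point using the time windows described in Table 17".
- Re-mapped data, whether unscheduled or early-termination, enter the analysis only where no scheduled value of the same parameter exists at that timepoint, and "only if the data are scheduled to be collected at that analysis timepoint".

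Early-termination assessments after randomization skip the carry-back and go straight to the Table 17 windows.

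**The concern.** The carry-back should link a late or repeated test to the visit it belongs to. It does so only if it does not reach into the next visit. Here it reaches past the nominal day of each visit at which the primary endpoints are measured after baseline. A value obtained on the planned day of V16 can be labelled Month 11 and then dropped, because nothing in the smokers' health profile is scheduled at Month 11. The mixed model would treat that observed value as missing at random. V16 is the primary timepoint, and its numbers are already reduced because about 65% of randomized subjects enrolled in the extension.

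**Working it through.** **Inputs.** Nominal study days come from SAP Table 17: V5 29, V6 64, V7 92, V8 120, V9 155, V10 183, V14 302, V15 337 (the entry begins "337 (V15, Week 48") and V16 365. The visit window is ±5 days (SAP Table 15). For V16, Protocol Section 4.1 gives "V16 (52 weeks after V4, 364 days +/- 5 days"); with V4 as day 1, 364 days after V4 is study day 365. After baseline, the primary endpoints are analysed at V7, V10 and V16 (SAP 12.7.1.2). Lung function and cardiovascular markers (12.7.2.4.1) and the safety laboratory panel that supplies WBC (12.7.4.3) are listed at the same visits. Section 12.7.4.3 also speaks of summarizing laboratory data from V5 to V16, but the Appendix 1 schedule has no laboratory draw from V11 to V15.

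**The SAP's own example.** Laboratory tests missed at V7 and done on day 123 are not Month 3, "because performed 31 days later than nominal V7 study day". Check: 92 + 30 = 122, and 123 > 122, so Table 17 applies. Day 123 lies in 107–137, which is Month 4. Day 122 would have been Month 3. The example reproduces.

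**Gaps.** 92 − 64 = 28; 183 − 155 = 28; 365 − 337 = 28. All are below 30.

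**Preceding visit recorded, target visit not recorded on or before the unscheduled date:**

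| Target | Reference | Cut-off | In-window days | Sent back | Label |
|---|---|---|---|---|---|
| V7 | V6 | 64 + 30 = 94 | 87–97 | 87–94 (8 of 11) | Month 2 |
| V10 | V9 | 155 + 30 = 185 | 178–188 | 178–185 (8 of 11) | Month 5 |
| V16 | V15 | 337 + 30 = 367 | 360–370 | 360–367 (8 of 11) | Month 11 |

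The other 3 days in each window (95–97, 186–188, 368–370) map correctly. Table 17 alone places all 11 days in Month 3, 6 or 12. Measured against the Table 17 windows, the days overridden are 79–94, 170–185 and 352–367, 16 days each.

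**Neighbouring cases.**

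- Target visit recorded on or before the unscheduled date: the reference is V7, V10 or V16 itself. Every day up to its nominal day + 30 maps correctly, and nothing is lost.
- Preceding visit also not recorded: the reference is V5 (29 + 30 = 59), V8 (120 + 30 = 150) or V14 (302 + 30 = 332). Table 17 applies and all 11 days map correctly.

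So with V15 on record and V16 not, a day-365 value is dropped and a day-368 value is kept. A subject who missed V15 as well keeps the day-365 value. Spirometry on day 360 counts as Month 12 on an early-termination form but is lost on an unscheduled form.

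**The case against.** The strongest reply is that the algorithm is written for repeated or delayed assessments, where the target visit normally exists already. That is correct. The main foreseeable repeat, spirometry redone within 7 days of V16 (Protocol 7.3.5.1), takes V16 as its reference and is kept. Tests done inside the V16 window would ordinarily be entered as V16, so the triggering pattern is unusual. Subjects who discontinue are covered by the Table 17 mapping of early-termination data. Extension entry requires a completed V10, so for those subjects only values dated before the recorded V10 could be affected. The rule takes no account of arm or product use, and a pre-analysis data review precedes database lock.

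These points limit how often the rule misfires; they do not make the assignment right. The SAP itself expects missed visits (Table 14 has a category for a scheduled visit not done), and this algorithm is its stated means of keeping data held on unscheduled forms. It gives no reason for the carry-back to override Table 17 within the next visit's window.

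A reader might infer that every on-time primary-endpoint value on an unscheduled form is lost. The documents do not support that: both conditions must hold, and even then 3 of the 11 days are safe.

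**Conclusion.** The rule gives a wrong assignment in a defined situation: preceding visit recorded, target visit not recorded on or before the unscheduled date, and no scheduled value of that parameter at the target visit. In that situation 8 of 11 in-window days are lost at V7, V10 or V16. The exposure that matters is at V16 and V7; at V10 it is narrow.

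This rests on reading a recorded visit as one on file on or before the unscheduled date. It also assumes that no primary endpoint is collected at V6 or V9. The SAP's visit lists support that, but the original study's assessment tables are not among the documents.

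The number of values affected is not given and is probably small. A reader might infer a material loss of V16 data. For scale only, 65% of 950 is about 618 subjects, so each 1% meeting the conditions would be about 6 subjects; the documents support no particular percentage. Nor do they show any effect on the primary conclusion. This is a programming-rule error worth correcting before lock, not a threat to the analysis as a whole.

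**What to change.** In step 3 of SAP Section 12.1.6, assign data to the reference scheduled visit only if the parameter is scheduled to be collected at that visit; otherwise map by the Table 17 window. This takes one sentence and one condition in the derivation program. A day-365 spirometry value then becomes Month 12. The day-123 example stays at Month 4, and repeats after a recorded V7, V10 or V16 are unchanged.

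There is a small downside. Unscheduled values from days 79–86, 170–177 or 352–359, before the ±5-day window, could fill an otherwise empty Month 3, 6 or 12 value; an ad hoc safety blood draw supplying WBC is the obvious case. Table 17 already allows this for early-termination data. If it is unwanted, the listings can flag such values for the data review.

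The condition does not help parameters collected at both visits, such as blood pressure at V15 and V16, which would still go to Month 11. Shortening the carry-back to 14 days would cover those too, since 64 + 14 = 78, 155 + 14 = 169 and 337 + 14 = 351 are the ends of the Month 2, 5 and 11 windows. But it would also give up late V7 repeats on days 107–122, which the present rule keeps. The conditional wording is therefore preferable.

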**Table 17: Mapping of Visits After Randomization**

Analysis Time Point	Nominal Study Day (Study Visit and Week number)	Time Window (in Study Days) for Assessments
Day 1	1	= 1
Month 1	29 (V5, Week 4)	[2, 46]
Month 2	64 (V6, Week 9)	[47, 78]
Month 3	92 (V7, Week 13)	[79, 106]
Month 4	120 (V8, Week 17)	[107, 137]
Month 5	155 (V9, Week 22)	[138, 169]
Month 6	183 (V10, Week 26)	[170, 197]
Month 7	211 (V11, Week 30)	[198, 228]
Month 8	246 (V12, Week 35)	[229, 260]
Month 9	274 (V13, Week 39)	[261, 288]
Month 10	302 (V14, Week 43)	[289, 319]
Month 11	337 (V15, Week 48)	[320, 351]
Month 12	365 (V16, Week 52)	≥ 352

Unscheduled assessments will be labelled as unscheduled and presented together with the re-mapped analysis time point in the listings.

Early Termination Assessments will be mapped using the relative study day using the visit date until midnight. Given that Early Termination visits are in general conducted during scheduled visits, the mapping will be performed using time windows as defined in Table 17, apart from early termination visits before randomization (e.g. subjects enrolled and not randomized) which will be assigned to the Enrollment time point. Early termination visit assessments will be labelled as early termination visit and presented together with the re-mapped analysis time point in the listings.

Data from Unscheduled and Early Termination assessments will be combined with data from scheduled visits in the analysis and summary statistics only if there are not scheduled visit

data for the same parameters at that re-mapped analysis time point, and only if the data are scheduled to be collected at that analysis timepoint.

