7.3.5 Other Clinical Assessments

7.3.5.1 Lung Function Testing

All personnel performing lung function testing must have the appropriate training. In addition QC measures should be put into place and be properly documented and filed at the pulmonary function laboratory (including the records of the calibration, if applicable). A certified study site staff should perform the assessment and the results will be assessed by a pulmonologist. The subject will be at rest for at least 15 minutes prior to lung function testing. All lung function manoeuvres will be recorded with the subject in a sitting position throughout the study.

All lung function tests will be managed by a central provider, including the provision of equipment and site manual.

All lung function data will be reviewed by blinded over-readers and the acceptability of the overall sessions and individual tests will be provided to the Investigator.

At the end of each appropriate visit the certified study site staff will be required to send the lung function data to the central provider.

Spirometry Testing

The spirometry test will be performed in accordance with the 2005 guideline of the American Thoracic Society (ATS)/European Respiratory Society (ERS) Joint Task Force on the standardization of spirometry [35]. Spirometry predicted values will be standardized to the Third National Health and Nutrition Examination Survey (NHANES III) predicted set.

Confidentiality Statement

Data and information contained in this document are considered to constitute trade secrets and confidential commercial information, and the legal protections provided to such trade secrets and confidential information are hereby claimed under the provisions of applicable law. No part of this document may be publicly disclosed without the written consent of Philip Morris Products S.A.

The spirometry tests will include the recording of FEV₁, FVC, FEV₁/FVC ratio and FEF 25-75.

All spirometry tests will be performed using the multi-breath (closed circuit) technique, as described in the Investigator pulmonary function testing (PFT) site manual. The PFT manual will include information on equipment, procedures, subject instructions and precautions.

All spirometry tests must be performed 1 hour after smoking or using THS 2.2.

Each subject will need to begin their spirometry tests in a time window of +/- 2 hours respective to the time of the spirometry tests done at V3 (Baseline) during the original study.

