Pre- and Post-Bronchodilator Spirometry Testing:

- At V16:

Pre- and post-bronchodilator spirometry test will be performed. Values for FEV₁, FVC, and FEF 25-75 will be recorded. The ratio FEV₁/FVC will be calculated from the highest acceptable FEV₁ and the highest acceptable FVC respectively. At V16, pre- and post-bronchodilator spirometry will be used to describe the changes in pre- and post-bronchodilator spirometry measurements over the duration of the study.

All post-bronchodilator spirometry testing will be performed 15-30 minutes post administration of around 400 µg of salbutamol (usually equivalent to 4 puffs assuming 100 µg/puff). The time of salbutamol inhalation and time of spirometry assessment will be recorded in the source document.

At V16, in case the value of the pre- and post-bronchodilator spirometry test(s) do not meet the ATS/ERS criteria the subject will need to come back within a 7 day window to repeat the test(s).

Lung Volume Measurements Using Multiple Breath Helium Dilution Technique:

At V16: lung volume measurements will be conducted as part of the lung function tests and the following values will be recorded: VC, functional residual capacity (FRC), IC and TLC. If required, a second test can be performed. Between tests, a minimum waiting time of 4 minutes is required. For FRC, the mean value will be used if more than one attempt is performed. TLC is evaluated as FRC plus IC. VC will be the highest from FRC-He if more than one attempt is performed. RV will be calculated as TLC minus VC_{max}. VC_{max} is the highest from FRC-He wash in.

All lung volumes measurements will be done pre-bronchodilator as outlined in Appendix 1. The PFT manual will include information on equipment, procedures, subject instructions and precautions.

The helium dilution technique will be used in accordance with the recommendations of the ATS/ETS Joint Task Force on the standardization of the measurement of lung volumes [36]. This technique is a closed-circuit system where a spirometer is filled with a mixture of helium

Confidentiality Statement

Data and information contained in this document are considered to constitute trade secrets and confidential commercial information, and the legal protections provided to such trade secrets and confidential information are hereby claimed under the provisions of applicable law. No part of this document may be publicly disclosed without the written consent of Philip Morris Products S.A.

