9.4 Early Termination Procedures

The following early termination procedures will be performed within 5 days of the date of study discontinuation, if a subject is discontinued from the study:

- AE/SAE recording.
- Clinical laboratory parameters (hematology, clinical chemistry, and urine safety analysis).
- Physical examination.
- Lung function (spirometry pre-bronchodilator and spirometry post-bronchodilator). In case the value of the test(s) do not meet the criteria the subject will need to come back within a 7 day window to repeat the test(s).
- Urine pregnancy.
- Vital signs.
- ECG.
- Information on the risk of smoking, smoking cessation advice, and debriefing on THS 2.2.

If the early termination visit occurs on the same day than a planned visit (e.g. the subject wants to withdraw or is discontinued in the middle of V12), all assessments that have been performed during the planned visit should not be conducted again for the ET procedures. In case an early

Confidentiality Statement

Data and information contained in this document are considered to constitute trade secrets and confidential commercial information, and the legal protections provided to such trade secrets and confidential information are hereby claimed under the provisions of applicable law. No part of this document may be publicly disclosed without the written consent of Philip Morris Products S.A.

termination visit is not performed, the subject will still enter into the 28 days Safety Follow-up Period after the discontinuation date.

Confidentiality Statement

Data and information contained in this document are considered to constitute trade secrets and confidential commercial information, and the legal protections provided to such trade secrets and confidential information are hereby claimed under the provisions of applicable law. No part of this document may be publicly disclosed without the written consent of Philip Morris Products S.A.

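### As written, SAP 12.1.6 can keep a V16 spirometry value that failed ATS/ERS criteria and drop the repeat the protocol requires, which affects primary FEV1 %pred

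*SAP*

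**What the plan says.** Protocol 7.3.5.1 sets up quality control for lung function. A central provider manages the tests, blinded over-readers review all data, and "the acceptability of the overall sessions and individual tests will be provided to the Investigator". If V16 pre- or post-bronchodilator results "do not meet the ATS/ERS criteria the subject will need to come back within a 7 day window to repeat the test(s"). Protocol 9.4 has the same requirement for early termination visits.

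On what is kept, the protocol says only "Values for FEV₁, FVC, and FEF 25-75 will be recorded" at V16. The word acceptable is attached to the ratio alone: "The ratio FEV₁/FVC will be calculated from the highest acceptable FEV₁ and the highest acceptable FVC respectively".

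SAP 12.1.6 generally excludes unscheduled assessments but makes an exception because "certain data planned for scheduled assessments are reported within unscheduled visit forms in the eCRF", with repeated or delayed assessments as its example. It says that moving these data to the scheduled visit in the eCRF is impractical, so a re-mapping algorithm will bring them into the analysis. The closing paragraph, after Table 17, then restricts this: unscheduled and early termination data are "combined with data from scheduled visits in the analysis and summary statistics only if there are not scheduled visit" data for the same parameters at the re-mapped time point.

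Post-bronchodilator FEV1 %pred at V16 is one of the eight primary endpoints (SAP 5.1). It is the only one with a numerical precision statement (SAP 8), and Protocol 4.2 says it will receive particular interest.

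**The concern.** The re-mapping rule and the precedence rule suit a delayed assessment, where nothing was recorded at the scheduled visit. The SAP's worked example is of that kind: laboratory tests missed at V7 and done later. A repeat is different, because it normally follows a test that was done. If the first test left a value, the precedence rule selects that value, and the stated aim of accounting for repeated assessments fails for the repeats themselves.

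For V16 spirometry this means that a subject can be brought back under the protocol's quality rule, produce an acceptable test, and still be represented in the primary model by the failed one. At stake are the validity of the V16 FEV1 value in the primary FAS-EX analysis, the secondary spirometry endpoints in SAP 12.7.2.4.1, and clear pre-specification in an open-label study of which session supplies the endpoint.

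**Working it through.** **1. Reproduce the SAP's own example.** An unscheduled assessment at day 123 follows V7, nominal day 92. The limit is 92 + 30 = 122. Since 123 > 122, the assessment goes to the Table 17 window containing day 123, which is [107, 137], Month 4. This agrees with SAP 12.1.6; day 122 would have stayed at Month 3.

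**2. Apply the same algorithm to a V16 repeat.**
- V16 is 364 ± 5 days after V4 (Protocol 4.1). With V4 as Day 1, that is study day 360 to 370.
- A repeat within 7 days therefore falls no later than 370 + 7 = 377.
- The limit for V16 is 365 + 30 = 395.
- Since 377 ≤ 395, every permitted repeat maps to Month 12. A later one would as well, because the Month 12 window in Table 17 is open-ended (day 352 onward).

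**3. Apply the precedence rule.**
- Scheduled V16 FEV1 present (failed), repeat on an unscheduled form: the scheduled, failed value is used.
- Scheduled V16 FEV1 absent, repeat on an unscheduled form: the repeat is used.

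**4. Look for a rule that reverses step 3.**
- SAP 12.1.4 covers missing values and quantification limits, not test quality.
- SAP 10.1 asks for a valid value, but only for population membership, and does not define valid.
- SAP Tables 13 and 14 have no category for spirometry acceptability. Deviations in any case exclude data from the PP analysis, not from FAS-EX.
- Protocol 7.3.5.1 sends the over-read result to the Investigator. No analysis rule uses it.

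**5. Precision context.** The documents give no failure rate, so this step is a sensitivity calculation on assumed values. For a two-group comparison, half-width = t(0.975, n1 + n2 − 2) × SD × √(1/n1 + 1/n2), with SD 6.4 %pred from SAP 8.
- Original planning assumptions: n1 = 475 × 0.70 × 0.50 = 166 and n2 = 475 × 0.70 = 332. The half-width is 1.965 × 6.4 × √(1/166 + 1/332) = 1.195.
- Revised assumptions, applying both the 65% enrolment and the 20% loss: n1 = 475 × 0.65 × 0.80 × 0.60 = 148 and n2 = 475 × 0.65 × 0.80 = 247. The half-width is 1.966 × 6.4 × √(1/148 + 1/247) = 1.308.
- Both are below 1.5, with probability above 99% when sampling variation in the SD is allowed for. The plan's statement is consistent with its inputs.

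Now suppose a fraction f of V16 values comes from failed tests with extra error SD e, so that SD′ = √(6.4² + f·e²), on the revised numbers:

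| f | e (%pred) | SD′ | Half-width | Probability ≤ 1.5 |
|---|---|---|---|---|
| 0.05 | 5 | 6.50 | 1.33 | >0.99 |
| 0.05 | 10 | 6.78 | 1.39 | 0.99 |
| 0.10 | 5 | 6.59 | 1.35 | >0.99 |
| 0.10 | 10 | 7.14 | 1.46 | 0.79 |
| 0.20 | 10 | 7.81 | 1.60 | 0.05 |

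A shift in the contrast would also need failure rates to differ between groups. With a difference Δ and a mean error d in failed tests, the shift is Δ × d. For illustration, Δ = 0.05 with d = 4 to 10 %pred gives 0.2 to 0.5 %pred; neither figure is in the documents.

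**The case against.** The strongest reply is that SAP 12.1.6 never mentions spirometry, so a reader who concludes that the plan always discards repeat tests goes further than the text. The outcome needs two conditions: the failed FEV1 is held as scheduled V16 data, and the repeat is on an unscheduled form. Lung function has its own route through a central provider, which also derives the predicted values (SAP 12.7.2.4.1). If that provider withholds unacceptable values, or the repeat is transferred as V16, the repeat is analysed. The lung function manual and the data management plan may settle this, but they are not part of these documents. This stands as a limit on the claim. It does not remove it: neither document describes such a safeguard, and SAP 12.1.6 calls it impractical to re-assign these data to the scheduled visit in the eCRF.

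The deviation lists are stated to be non-exhaustive, a pre-analysis data review is planned (SAP 13.4), and Listing 15.3.2.4 will show excluded observations. Failed sessions may therefore be noticed. None of these gives a rule for FAS-EX, and settling the choice case by case at data review is weaker than a written rule.

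A failed session need not make its FEV1 unusable, since the over-read grades overall sessions and individual tests separately. This is a fair argument against blanking every failed value in the primary analysis. It is also tempting to extend the point to COPD staging, but staging is first gated by FEV1/FVC, and the protocol already takes that ratio from acceptable values.

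**Conclusion.** The concern holds in conditional form. As written, SAP 12.1.6 ranks a failed scheduled V16 spirometry value above its acceptable repeat whenever the first is held as scheduled data and the second as unscheduled data, and no rule governing FAS-EX reverses this. That works against the protocol's own quality-control step for a primary endpoint.

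Two stronger readings are not supported. A reader might infer that FEV1 will be biased downward because poor efforts read low; the documents say nothing about the direction of error, or about failure rates differing between groups. A reader might also infer that the ±1.5 %pred target is lost. With 5–10% failed values and extra error SD of 5–10 %pred, the expected half-width stays below 1.5. Only at the harsher end does the probability of meeting the target fall under the stated 90% (0.79 at 10% and 10 %pred), and the half-width exceeds 1.5 only in the more extreme 20% case. The target is probably still met. The reason to act is data validity and pre-specification; the true size of the effect is unknown.

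**What to change.** Add to SAP 12.1.6 that, for V16 spirometry, an acceptable repeat obtained within the protocol's 7-day window replaces a scheduled test that the blinded over-read graded as not meeting ATS/ERS criteria. Report the number of replaced values, and of failed sessions without an acceptable repeat, by product use category and by arm. For failed sessions without an acceptable repeat, keep the primary handling and add a sensitivity analysis that sets those values to missing in the MMRM.

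Leave V7 and V10 values as handled in the original study, which has its own SAP; changing them here would work against the consistency with its results that SAP 9 seeks.

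The cost is one extra programming step and the need to carry the over-read acceptability grade into the analysis dataset. If the data flow already prevents the problem, a sentence saying so is enough to settle which test is analysed.
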